8.2 Comparability of Subjects at Baseline

The statistical significance of any treatment group difference in the distribution of categorical variables such as gender will be tested using Cochran–Mantel–Haenszel (CMH) test for general association adjusted for site. Continuous variables, such as age, will be analyzed using a two-way analysis of variance (ANOVA) model with site and treatment as a fixed effect.

9. CONSENT/ASSENT CONSIDERATIONS AND PROCEDURES

It will be made clear to the subject that, for the purposes of the study, they are consenting only for topical application of medication or vehicle. Investigators may discuss the availability of the study and the possibility for entry with a potential subject without first obtaining consent/assent. However, informed consent/assent must be obtained and documented prior to initiation of any procedures that are performed solely for the purpose of determining eligibility for research, including withdrawal from current medication(s). When this is done in anticipation of, or in preparation for, the research, it is considered to be part of the research.

The study must be approved in writing by an appropriate IRB as defined by FDA regulations. A copy of the Letter of Approval from the IRB, which also contains specific identification of the documents approved, must be received by Perrigo prior to study commencement.

Periodic status reports must be submitted to the IRB at least annually as required by the site's IRB, as well as notification of completion of the study and a final report within three months of study completion or termination. A copy of all reports submitted to the IRB must be sent to Perrigo.

The investigator(s) has both ethical and legal responsibility to ensure that each subject being considered for inclusion in this study is given a full explanation of the protocol. This shall be documented on a written informed consent/assent form, which shall be approved by the same Institutional Review Board (IRB) responsible for approval of this protocol. Each informed consent/assent form shall include the elements required by FDA regulations in 21 CFR Part 50.

Protocol No: PRG-NY-14-019

The investigator agrees to obtain approval from Perrigo of any written informed consent/assent form used in the study, preferably prior to submission to the IRB.

Once the appropriate essential information has been provided to the subject and fully explained by the investigators (or a qualified designee) and it is felt that the subject understands the implications of participating, the IRB-approved written informed consent/assent form shall be signed by the subject (or their parent/legally authorized representative) and the person obtaining consent/assent (investigator or designee). The subject shall be given a copy of the signed informed consent/assent form and the investigator shall keep the original on file.

If the subject fails to meet the inclusion/exclusion criteria at the conclusion of the screening phase, the subject will be withdrawn from screening. In the event that the subject is re-screened for study participation, a new informed consent/assent form must be signed.

9.1 Subject Confidentiality

All participants are concerned for the individual subject's privacy and, therefore, all subject data will be identified only by a subject identification number and subject initials. However, in compliance with federal guidelines regarding the monitoring of clinical studies and in fulfillment of his/her obligations to Perrigo, it is required that the investigator permit the study monitor, a Perrigo authorized representative, and/or FDA representative to review that portion of the subject's medical record that is directly related to the study. This shall include all study relevant documentation including subject medical histories to verify eligibility, laboratory test result reports to verify transcription accuracy, admission/discharge summaries for hospital stays occurring while the subject is enrolled in the study and autopsy reports for deaths occurring during the study.

As part of the required content of informed consent, the subject must be informed that his/her medical chart may be reviewed by Perrigo, Perrigo authorized representative, or a representative of the FDA. Should access to the medical record require a separate waiver or authorization, it is the investigator's responsibility to obtain such permission from the subject in writing before the subject is entered into the study.

To preserve the subject's confidentiality, the data collected will be available only to the investigators of the study, their support staff, Perrigo, and possibly the FDA.

All reports and communications relating to the subject in the study will identify each subject only by the subject's initials and by the subject number. The investigator agrees to furnish Perrigo with complete subject identification, if necessary on a confidential follow-up form, which will be used for the purpose of a long-term follow-up, if needed. This will be treated with strict adherence to professional standards of confidentiality and will be filed at Perrigo under adequate security and restricted accessibility.

10. RECORDS MANAGEMENT

10.1 Data Collection

Database set-up will be performed by [REDACTED] in collaboration with the Electronic Data Capture (EDC) vendor, using an appropriate fully validated, 21 CFR Part 11 compliant Electronic Data Capture (EDC) system. eCRFs will be provided to each site via a secured web link. All applicable study data collected on each subject will be recorded by approved site personnel into the eCRF. Only authorized site personnel will be able to enter/modify/correct data to the eCRF.

Approved staff at [REDACTED] will verify all data entered into eCRFs for completeness and accuracy with reference to the source documents and records and will issue manual data queries to correct missing data or discrepancies found against the source within the EDC system.

Data validation will consist of automated and manual edit checks that are created directly into EDC. Automated edit checks will be executed on all data points defined and documented by the study team and data management. Study metrics will be reported from the EDC system.

After all data have been verified by approved staff at [REDACTED], an Investigator or Sub-Investigator (listed on Form FDA 1572) is required to review and approve all eCRFs prior to database lock and breaking of the blind.

After database lock, each site will be provided with a CD that will include the eCRF data from their site for local archival purposes.

Quality assurance verification via a 10% database audit of eCRF data will be conducted before the treatment assignment code is broken.

10.2 Source Documents

Source documents are defined as the results of original observations and activities of a clinical investigation. Source documents will include, but are not limited to, progress notes and screening logs. All source documents pertaining to this study will be maintained by the investigators and made available for inspection by authorized persons. The original signed informed consent form for each participating subject shall be filed with records kept by the investigators and a copy given to the subject.

10.3 File Management at the Study Site

It is the responsibility of the investigator to ensure that the study center file is maintained in accordance with Section 8 of the International Conference on Harmonization (ICH) Guideline for Good Clinical Practices (GCP).

10.4 Records Retention at the Study Site

FDA regulations require all investigators participating in clinical drug studies to maintain detailed clinical data for one of the following periods:

Protocol No: PRG-NY-14-019

- a) A period of at least two years following the date on which a New Drug Application is approved by the FDA;
- b) A period of two years after Perrigo New York notifies the investigator that no further application is to be filed with the FDA.

The investigator must not dispose of any records relevant to this study without either (1) written permission from Perrigo New York or (2) providing an opportunity for Perrigo to collect such records. The investigator shall take responsibility for maintaining adequate and accurate electronic or hard copy source documents of all observations and data generated during this study, including any data clarification forms (DCFs) received from Perrigo. Such documentation is subject to inspection by Perrigo and the FDA.

11. QUALITY CONTROL AND QUALITY ASSURANCE

11.1 Monitoring

Perrigo has ethical, legal and scientific obligations to carefully follow this study in a detailed and orderly manner in accordance with established research principles and FDA regulations. All medical records (source documents) of the subjects participating in this study must be presented for review and verification of eCRFs.

11.2 Auditing

Perrigo (or representative) may conduct audits at the study center(s). Audits will include, but are not be limited to, drug supply, presence of required documents, the informed consent process, and comparison of case report forms with source documents. The investigator agrees to participate with audits conducted at a reasonable time in a reasonable manner.

Regulatory authorities worldwide may also audit the investigator during or after the study. The investigator should contact Perrigo New York immediately if notified of such an audit, and must fully cooperate with the audits conducted at a reasonable time in a reasonable manner.

12. ETHICS AND RESPONSIBILITY

This study must be conducted in compliance with the protocol, the United States Food and Drug Administration (FDA) regulations, any other countries regulations, and ICH GCP Guidelines.

Appendix B: [REDACTED]

[REDACTED]

[REDACTED]

[REDACTED]

[REDACTED]

[REDACTED]

[REDACTED]

[REDACTED]

[REDACTED]

[REDACTED]

[REDACTED]

[REDACTED]

[REDACTED]

[REDACTED]

[REDACTED]

[REDACTED]

[REDACTED]

[REDACTED]

[REDACTED]

[REDACTED]

[REDACTED]

[REDACTED]

[REDACTED]

[REDACTED]

[REDACTED]

[REDACTED]

[figure not shown]
[REDACTED]

[REDACTED]

[figure not shown]
[REDACTED]

[REDACTED]

6.2 Summary of Assessments9

[REDACTED]

[REDACTED]

[REDACTED]

[REDACTED]

List of Abbreviations

AE	Adverse Event
AK	Actinic Keratosis
ANOVA	Analysis of Variance
CI	Confidence Interval
CMH	Cochran-Mantel Haenszel
IGA	Investigator's Global Assessment
ITT	Intent-to-treat (population)
LOCF	Last Observation Carried Forward
MedDRA	Medical Dictionary for Regulatory Activities
mITT	Modified Intent-To-Treat (population)
PD	Protocol Deviation
PP	Per-protocol (population)
PV	Protocol Violation
SAE	Serious Adverse Event
SAP	Statistical Analysis Plan
TEAE	Treatment-Emergent Adverse Event
TESAE	Treatment-Emergent Serious Adverse Event
WHO Drug	World Health Organization Drug Dictionary

[REDACTED]

Statistical Analysis Plan

1 Purpose of Statistical Analysis Plan

The purpose of the statistical analysis plan is to describe in detail all the data, statistical methods, and summary tables required to implement the statistical analysis of Clinical Study Protocol PRG-NY-14-019 [REDACTED]

[REDACTED]

2 Study Objectives

To compare the safety and efficacy profiles of Perrigo UK FINCO Ingenol Mebutate Topical Gel 0.015% to Picato® Topical Gel 0.015% (Ingenol Mebutate Topical Gel 0.015%) and to demonstrate the superior efficacy of the two active formulations over that of the vehicle in the treatment of Actinic Keratosis.

3 Study Design

For the purpose of exploring the above objectives, the study will be conducted as a double-blind, randomized, parallel-group, vehicle-controlled, multicenter trial.

The actual number of subjects enrolled in the study will be based on blinded review of subject status (related to the modified intent-to-treat (mITT) definition and the per-protocol (PP) definition under Section 4 to determine that the size of enrollment is adequate to obtain a sufficient number of subjects meeting the mITT criteria [REDACTED] and a sufficient number of subjects meeting the PP criteria [REDACTED]. If this number is expected to be met prior to enrolling [REDACTED] subjects, the enrollment will be closed.

[REDACTED]

[REDACTED]

Each subject will be randomly assigned to one of following treatment groups [REDACTED]:

- (1) Test: Ingenol Mebutate Topical Gel 0.015%, Perrigo [REDACTED].
- (2) Reference: Picato® Topical Gel 0.015% (Ingenol Mebutate Topical Gel 0.015%), Leo Pharma Inc.

[REDACTED]

- (3) Vehicle of test product, Perrigo [REDACTED].

Subjects will be admitted into the study only after written informed consent has been obtained and all of the inclusion and none of the exclusion criteria have been met. Randomization will be performed according to a computer generated randomization scheme where the treatment group designation has been assigned to the subject number. The treatment designation will remain blinded until the final database is closed. An independent third party generator will generate and hold the randomization code throughout the study. Randomized subjects will apply assigned treatment medication topically by spreading evenly [REDACTED] to the designated treatment area (up to one contiguous skin area of approximately 25cm² on the head region (face or scalp) once daily for three (3) consecutive days, avoiding contact with the eyes, mouth and other body areas during and after gel application.

Subjects will be scheduled for an office visit for Visit 1/Day 1 (Baseline), Visit 2/Day 4 (+1 days) (Post-Treatment Interim), Visit 3/Day 29 (±3 days) (Interim), and Visit 4/Day 57 (±2 days) (End of Study). Safety will be assessed by monitoring adverse events at each visit and during a Follow-Up Phone Call/Day 15 (±3 days).

4 Populations To Be Analyzed

Three subject populations are defined as follows:

- (1) An intent-to-treat (ITT) subject is any individual who: (a) was randomized into the study, and (b) received and applied at least one dose of study medication;
- (2) A modified intent-to-treat (mITT) subject is any individual who: (a) was randomized into the study, (b) met eligibility criteria, (c) received and applied at least one dose of study medication, and (d) had at least one post-baseline efficacy assessment;
- (3) A per-protocol (PP) subject, consistent with the protocol, is one that: (a) met eligibility criteria, (b) was randomized into the study, received and used study medication, (c) applied the study medication on Days 1-3 [REDACTED] (d) completed Visit 4/Day 57 (End of Study/Early Termination Visit) within the ±2 days visit window OR was discontinued from the study due to treatment failure [REDACTED] and (e) without significant protocol violations that could have interfered with the administration of the treatment or the precise evaluation of treatment efficacy.

[REDACTED]

[REDACTED]

5 Planned Analyses

5.1 Methodological Considerations

The study will be conducted under the same protocol across all the sites. No formal statistical analyses are planned to evaluate the consistency of efficacy results across the multiple clinical sites. These results, however, will be tabulated and if a site's efficacy data are obviously inconsistent with the results across all sites, this will be explored and addressed in the final study report.

Two-sided hypothesis testing will be conducted for all the tests. Resulting p-values less than 0.05 will be considered statistically significant unless noted otherwise. No adjustments of p-values for multiple comparisons will be made. No interim analyses are planned. SAS software will be used for all data analyses and tabulations.

5.2 [REDACTED]

5.3 Demographics and Baseline Characteristics

Baseline variables (e.g., sex, age, ethnic origin) will be evaluated, adjusting for site, to identify differences between treatment groups, which were not eliminated by randomization. Any significant baseline differences will be reviewed for their potential impact on the efficacy findings.

Continuous variables at baseline will be examined by two-way analysis of variance (ANOVA) with treatment and site as fixed effects when normal error and homogeneous variance assumptions are satisfied, or by the nonparametric rank based ANOVA when they are not, to compare treatment group differences.

Categorical variables such as gender, race, etc., will be examined by Cochran-Mantel-Haenszel test, stratified by site.

Summary tables by treatment group will be presented. For each continuous variable, the summary will include the mean, standard deviation, minimum and maximum. For each categorical variable, the summary will include frequencies and percentages.

5.4 Subject Accountability

A summary of subject disposition will be provided for all subjects. Descriptive summaries of subject disposition, reason for discontinuation, and analyses population will be provided by treatment group. The data will also be presented in subject data listings.

5.5 Efficacy Variables and Analyses

The primary efficacy measure is the proportion of subjects with clinical response of success defined as complete clearance (absence) of all clinically visible Actinic Keratosis lesions identified at the baseline visit and no new Actinic Keratosis lesions in the treatment area at Visit 4/Day 57.

Equivalent Efficacy

The compound hypothesis to be tested for clinical equivalence between test and reference is:

$$H_0: p_T - p_R < -0.20 \text{ or } p_T - p_R > 0.20 \text{ versus}$$

$$H_A: -0.20 \leq p_T - p_R \leq 0.20.$$

Where p_T and p_R are the proportions of subjects with clinical success at Visit 4/Day 57 for the test and reference products, respectively. The test product will be considered to be clinically equivalent to the reference product if the 90% confidence interval (CI) on the difference in their rates of clinical success, calculated by the Wald's method with Yates' continuity correction, is contained within the limits -0.20 to +0.20 for the PP population. Rejection of the null hypothesis supports the conclusion of therapeutic equivalence between the test and reference products for the primary efficacy variable.

[REDACTED]

Superiority

The hypotheses to be tested for superiority of the test and reference products over vehicle are:

$$H_0: p_T \leq p_V \text{ versus } H_A: p_T > p_V$$

$$H_0: p_R \leq p_V \text{ versus } H_A: p_R > p_V$$

Where p_T , p_R and p_V are the proportion of subjects with clinical success at Visit 4/Day 57 for the test, reference and vehicle products, respectively. The tests will be conducted independently for the test product and the reference product using two-sided, $\alpha = 0.05$, continuity-corrected Z-tests for the mITT subjects. Superiority will be established if the proportion of subjects with clinical success in the active treatment group is greater and statistically different than that in the vehicle. Rejection of the null hypothesis supports the conclusion of superiority of the test and reference products over the vehicle product for the primary efficacy variable.

[REDACTED]

5.6 Safety Variables and Analyses

Duration of Treatment and Medication Compliance

Number of applications, days of exposure, and compliance rate will be summarized by treatment group using descriptive statistics. For each subject, the overall duration of treatment (days) will be calculated using the following formula:

$$(\text{Date of last application of study medication}) - (\text{Date of first application of study medication}) + 1.$$

Medication compliance rate (%) will be calculated for each subject as follows:

$$(\text{Total number of applications used}) / (\text{Expected number of applications}) * 100\%.$$

Subjects who complete the study are expected to have 3 applications. Subjects will only be considered compliant if they apply all three daily doses on study Days 1-3. For prematurely discontinued subjects, expected number of applications will be determined based on the overall duration of treatment by the time of discontinuation. Descriptive summaries of exposure and medication compliance rate will be provided by treatment group for the ITT subjects

Adverse Events

Adverse events (AEs) will be coded in MedDRA, version 15.1. Treatment-Emergent Adverse Event (TEAE) is defined as any AE occurs on or after applying the first dose of study drug. Number and percent of subjects reporting TEAEs will be tabulated by treatment group. Summaries will be presented by body system and preferred term for the ITT population, and further by severity and relationship to study medication. [REDACTED]

[REDACTED] In the summaries of incidence rates (frequencies and percentages), severity and relationship to study drug, subjects who report more than one event that are mapped to the same preferred term will be counted only once under the strongest severity and relationship, accordingly Fisher's exact test will be used to compare the proportions of subjects of the two active treatment groups who report any TEAE.

Treatment-Emergent Serious Adverse Events (TESAEs) will be discussed within the clinical study report. TESAEs and TEAEs that led to treatment interruption or discontinuation will be presented in data listings.

Concomitant Medications

Concomitant medications will be coded using the WHO Drug Dictionary, version September 2014, and will be presented in data listings.

Application Site Reactions

The severity of application site reactions such as erythema, flaking/scaling, crusting, swelling, vesiculation/pustulation, and erosion/ulceration will be summarized by treatment group and visit using frequencies and percentages of subjects.

[REDACTED]

6 Appendices

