3 STUDY DESIGN

3.1 Type/Design of Study

Subjects in this multi-center, double-blind, randomized, vehicle-controlled, parallel-group study will be assigned [REDACTED] to test product, reference product, or vehicle, respectively. The study medication will be dispensed at Visit 1/Day 1 (Baseline) to subjects meeting all entry criteria. The assigned study medication will be applied topically [REDACTED] to the designated treatment area (up to one contiguous skin area of approximately 25cm² on the head region (face or scalp) once daily for three (3) consecutive days, avoiding contact with the eyes, mouth and other body areas during and after gel application.

Subjects will be healthy males and females, at least 18 years of age, with 4 to 8 clinically typical, visible and discrete, nonhyperkeratotic, nonhypertrophic Actinic Keratosis lesions within a contiguous 25cm² treatment area on the head region (face or scalp) excluding the nose. Visits to the study site are scheduled at Day 1 and Day 4, Day 29, and Day 57. There will also be a phone call at Day 15 to follow up on previously reported adverse events by the subjects.

At Visit 1/Day 1/Baseline written informed consent will be obtained. The subject's demographic profile, medical history, and prior/concomitant medication use will be recorded. A urine pregnancy test will be performed for all women of childbearing potential. A brief physical examination (including heart, lung and abdomen evaluations) including vital signs and height/weight will be recorded during baseline.

The subject's history of Actinic Keratosis will be evaluated at Visit 1/Day 1 (Baseline). A dermatological exam and Actinic Keratosis lesion assessment will be conducted at Visit 1/ Day 1(Baseline), and Visit 4/Day 57, and if necessary at an Unscheduled visit. Subjects who meet all of the inclusion and none of the exclusion criteria will be enrolled in the study, [REDACTED]

[REDACTED] and given a daily diary to complete. Instructions on proper treatment application and completion of the diaries will be provided to subjects and the rest of their visits will be scheduled. During the baseline visit, the study staff will demonstrate proper medication application to the subject and then observe the subject applying their initial application to ensure subjects understand the instructions. The study staff should instruct the subject to [REDACTED]

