5. PROCEDURES

5.1 Subject Screening and Enrollment

The study personnel will review the IRB approved informed consent form and assent form, if applicable, with each subject and give the subject an opportunity to have all questions answered before proceeding. The consent/assent form must be signed by each subject and witnessed before the subject is enrolled into the study. A copy of the signed consent/assent will be given to every participant and the original will be maintained with the participant's records. Subjects under the legal age of consent must sign an IRB approved written informed consent/assent in addition to a parent or legally authorized representative.

Subjects that require a wash-out [REDACTED] from their initial informed consent signing must be re-consented before any further study procedures can begin.

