7.2 Definitions

An adverse event (AE) is defined as any untoward medical occurrence in a patient administered a medicinal product and which does not necessarily have to have a causal relationship with this treatment. An adverse event can therefore be any unfavorable and unintended sign (for example, an abnormal laboratory finding), symptom, or disease temporally associated with the use of a medicinal product, whether or not considered related to this medicinal product.

A serious adverse event (SAE) is an adverse event that results in any of the following outcomes:

- death
- life-threatening event (i.e., the subject was, in the opinion of the investigator, at immediate risk of death from the event as it occurred. It does not include an event that, had it occurred in a more severe form, might have caused death)
- requires in-subject hospitalization or prolongs hospitalization
- a persistent or significant disability/incapacity or substantial disruption of the ability to conduct normal life functions
- congenital anomaly/birth defect
- Other adverse events that may be considered serious when, based upon appropriate medical judgment, they may jeopardize the patient or subject or may require medical or surgical intervention to prevent one of the previously listed outcomes.

Immediately Reportable Adverse Events (IRAE): Any serious AE or any AE that necessitates discontinuation of study medication, including pregnancy.

Unexpected Adverse Event: An unexpected event is any adverse drug experience, the specificity or severity of which is not consistent with the current approved product labeling (package insert, Appendix D) for the study medication, the Investigator's Brochure, or as described in the clinical protocol and consent materials.

Intensity of Adverse Events: The maximum intensity of an AE during a day should be recorded on the eCRF. If the intensity of an AE changes over a number of days, then separate entries should be made having distinct onset dates for the changes in severity.

Mild - AEs are usually transient, requiring no special treatment, and do not interfere with subject's daily activities.

Moderate - AEs typically introduce a low level of inconvenience or concern to the subject and may interfere with daily activities, but are usually ameliorated by simple therapeutic measures.

Severe - AEs interrupt a subject's usual daily activity and traditionally require systemic drug therapy or other treatment.

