7.3 Eliciting and Reporting of Adverse Events

The investigator will periodically assess subjects for the occurrence of adverse events. In order to avoid bias in eliciting adverse events, the subject or parent/legally authorized representative should be asked a non-specific question (e.g., "How have you been feeling since your last visit?") to assess whether any AE has been experienced since the last visit. All adverse events (as defined in Section 7.2), either observed by the Investigator or one of his/her medical collaborators, or reported by the participant spontaneously, or in response to direct questioning, will be reported and documented in the source and the study reporting forms. When reporting an adverse event, the Investigator must assign a severity grade to each event and declare an opinion on the relatedness of the event to the study medication or procedure. Serious or unexpected adverse events must be reported to Perrigo **within 24 hours** of when the Investigator first learns of the occurrence of the event.

Adverse events will be documented in source and recorded in a timely manner on eCRFs. Adverse events (i.e., worsening of Actinic Keratosis*) that are identified at the last assessment visit (or the early termination visit), must be recorded on the AE eCRF with the status of the AE noted.

* Worsening of the subject's Actinic Keratosis may be expected from application of the study medication. Therefore, this will only be identified as an adverse event if alternative treatment is required.

Adverse event reporting begins from the signing of informed consent/assent. Worsening of Actinic Keratosis from baseline will be considered a new adverse event and will be documented on the source document and eCRFs. Adverse events should be followed until resolved or 30 days after the final study treatment. In any case, serious adverse events that are not resolved or considered to be chronic within 30 days of the final study treatment must be followed by the investigator until they become resolved or are considered to be chronic (stabilized for at least 30 days). All events that are ongoing at this time will be recorded as ongoing on the eCRF.

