6.1 Handling of Missing or Incomplete Dates for Adverse Events and Concomitant Medications

Adverse Events

Handling of partial dates is only considered for the start date. An adverse event with a partial start date is considered treatment emergent if:

- only the day is missing and the start month/year is the same or after the month/year of the first dose
- the day and month are missing and the start year is the same or greater than the year of the first dose date
- the start date is completely missing

Concomitant Medications

Handling of partial dates is only considered for the stop date. A medication with a partial stop date is considered concomitant if:

- only the day is missing and the stop month/year is the same or after the month/year of the first dose
- the day and month are missing and the stop year is the same or greater than the year of the first dose date
- the stop date is completely missing or the medication is ongoing

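### The timing-only TEAE definition, combined with a new AE entry at every severity change, could flag a pre-dose AE that only becomes milder after dosing

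*SAP*

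**What the plan says.** Four provisions bear on this.

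- **Recording rule.** Protocol 7.2, on intensity, asks that "separate entries should be made having distinct onset dates for the changes in severity". The trigger is a change, with no restriction to an increase.
- **Start of collection.** Protocol 7.3: "Adverse event reporting begins from the signing of informed consent/assent". AEs that precede the first dose are therefore in the database.
- **TEAE definition.** SAP 5.6: "Treatment-Emergent Adverse Event (TEAE) is defined as any AE occurs on or after applying the first dose of study drug". It contains no condition that the event be new or worsened.
- **Date used.** SAP 6.1, on incomplete AE dates: "Handling of partial dates is only considered for the start date". It then compares the start month or year with that of the first dose.

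SAP 5.6 uses the flag for the incidence tables (by preferred term, severity and relationship) and for Fisher's exact test of test versus reference on the proportion of subjects with any TEAE. For repeated terms within a subject, it says that "more than one event that are mapped to the same preferred term will be counted only once under the strongest severity and relationship".

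**The concern.** The recording rule turns a change in severity into an entry with a new date, and the TEAE definition looks only at dates. An AE that was moderate before treatment and mild on Day 2 can then show a post-dose onset, although it began before the drug and is improving. Nothing visible in the SAP refers back to the first onset, to the pre-dose severity or to the direction of change. The problem arises with fully known dates, so it is separate from the partial-date rule.

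At stake is the accuracy of the TEAE tables. Falsely flagged events would raise incidence in whichever arm they fall. If they occur equally often in both active arms, they would also pull the any-TEAE comparison slightly towards no difference, which is the less cautious direction in a study meant to show comparable safety.

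**Working it through.** The plan states no figure on this point, so there is none to reproduce. The check applies the written rules to example histories and then asks who could be affected.

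**Step 1: classification.** Three rules are compared:

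- *Entry by entry*: flag if any entry has an onset on or after the first dose.
- *One event, timing only*: flag if the first onset is on or after the first dose.
- *New or worsened*: flag if the first onset is on or after the first dose, or if a post-dose severity exceeds that of the last pre-dose entry.

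| History | Entry by entry | One event, timing only | New or worsened |
|---|---|---|---|
| A. Began before dose, unchanged | no | no | no |
| B. Moderate before, mild after | **yes** | no | no |
| C. Mild before, moderate after | yes | **no** | yes |
| D. New after dose | yes | yes | yes |
| E. Moderate before, mild after, then moderate again | yes | no | no |

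B is the case at issue. The once-per-term rule does not remove it. That rule collapses several entries under one term, whereas B has only one post-dose entry and it still makes the subject positive.

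**Step 2: who can be affected.** Protocol 3.1: "At Visit 1/Day 1/Baseline written informed consent will be obtained". Under Protocol 5.11 the supervised first application takes place at the same visit. Protocol 2.2 asks for an approximate date of onset, and no visible text asks for a time. If dates are compared, an AE with onset earlier on Day 1 already falls on the first-dose date, and a later split entry changes nothing. The mechanism therefore adds a case only when onset was on an earlier day. That mainly means the group for whom Protocol 5.1 has a re-consent provision ("Subjects that require a wash-out"), since Protocol 9 requires consent before current medication is withdrawn. The interval is redacted. Protocol 5.10 also keeps the six listed application site reactions out of AE recording unless they lead to interruption, discontinuation or a new medication.

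**Step 3: effect on the any-TEAE comparison (illustration only).** Let p be the true any-TEAE rate in an arm and q the proportion with a falsely flagged event. Assume that q is equal in both arms and independent of true TEAEs. The observed rate is 1 − (1 − p)(1 − q), and the observed difference is the true difference × (1 − q). The rates of 30% and 20% and the values of q are assumed; none is in the documents.

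| q | Arm with p = 0.30 | Arm with p = 0.20 | Difference |
|---|---|---|---|
| 0 | 0.300 | 0.200 | 10.0 points |
| 0.01 | 1 − 0.70 × 0.99 = 0.307 | 1 − 0.80 × 0.99 = 0.208 | 9.9 points |
| 0.02 | 1 − 0.70 × 0.98 = 0.314 | 1 − 0.80 × 0.98 = 0.216 | 9.8 points |
| 0.05 | 1 − 0.70 × 0.95 = 0.335 | 1 − 0.80 × 0.95 = 0.240 | 9.5 points |

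Even at q = 5% the difference moves by only half a point.

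**The case against.** The strongest reply is that an eCRF entry is not an AE. Protocol 7.2 speaks of the intensity of one AE changing, the SAP defines a TEAE as an AE rather than an entry, and a fall from moderate to mild is not a new untoward occurrence. SAP 6.1 supports use of the start date but does not say which start date governs a split event. This stands as far as it goes: the text is open to two readings. It does not settle the matter, because under a timing-only definition the one-event reading fails the other way. It would leave out history C, a pre-dose AE that worsens after dosing.

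Redaction is a second reply. Text in SAP 5.6 close to the TEAE tabulation is blacked out and the eCRF design is not in the documents, so a handling rule or a link between entries cannot be excluded. That also stands, although the visible definition is a complete sentence with no exception.

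Third, inclusive flagging may be deliberate, since SAP 6.1 counts an AE with a wholly missing start date as treatment emergent. But that rule deals with unknown dates, whereas here the dates are known.

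A reader might infer three stronger claims, and the documents support none of them:

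- *Such events will certainly be counted as TEAEs.* This follows only from the entry-by-entry reading.
- *The number affected can be stated.* If 1–3% of subjects had an AE ongoing at first dose and half improved, the result would be 0.01 × 0.5 = 0.5% to 0.03 × 0.5 = 1.5%. Neither input has a source, and with consent and dosing normally on one day, 1–3% looks generous. The result would also apply per term. A subject with any genuine TEAE is already positive in the any-TEAE test.
- *Serious-event reporting is distorted.* That would need a serious AE before dosing in a subject still judged eligible and then dosed. Nothing in the documents points to such cases.

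**Conclusion.** The point holds as a gap in a definition. Under the visible text, a straightforward start-date derivation applied to split entries would flag a pre-dose AE that only improves after dosing. The conclusion rests on reading the definition entry by entry and on the redacted text containing no contrary rule.

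The effect is probably very small. It is confined in practice to subjects whose AE began on a day before the first dose, mainly those who went through a wash-out, and their number cannot be derived from the documents. Preferred-term incidence is the main output affected. The any-TEAE Fisher test is affected less, and no effect on treatment-emergent serious events is shown. Efficacy conclusions are untouched. This is a desirable clarification, not an obstacle to the analysis.

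**What to change.** In SAP 5.6, define a TEAE as an AE that first starts on or after the first dose, or one that was present before the first dose and afterwards exceeds its severity at first dose, taken from the last pre-dose entry. Add that entries created under Protocol 7.2 for changes in severity are treated as one event for this flag, so that an entry showing only reduced severity keeps the parent event's onset date. Linking the entries needs either an eCRF field or a derivation rule.

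The comparator must be named. Without it, history E (moderate, mild, moderate again) could be flagged or not depending on which entry is taken as the baseline. With the last pre-dose entry as comparator, a post-dose return to, but not above, the pre-dose severity is not flagged. Such cases should be listed so that a flare after dosing remains visible.

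The cost is a sentence or two in the SAP, a small extra derivation and one listing. Visits, endpoints and sample size do not change. The wording should be fixed before the blind is broken.
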